4.2.1.2 Handling of Missing Data for Secondary and Other Efficacy Endpoints

Missing data and intercurrent events for secondary and other efficacy endpoints will be handled as summarized in Table 4–1. Details of the imputation methods are described below and details of the statistical analyses and estimands are described in Section 8.2.2, Section 8.2.3, Section 8.3.2 and Section 8.3.3.

For composite binary secondary or other endpoints, the MI will be implemented on each component variable, before deriving the binary endpoint based on the imputed components (See Section 4.2.1.4.2). For each component, multiple imputation will use all visits where the individual component is planned to be collected. However, the binary endpoint will be derived (or presented in by-visit tables) only for those visits where **all** components are planned to be conducted per study protocol. In addition:

- ASAS20, ASAS-PR, and ASAS5/6 will follow the ASAS40 rules for when Baseline is equal to zero or baseline is missing as described in Section 4.2.1.1.
- For ASAS20, if at least 3 of the 4 components have observed data collected, the ASAS20 response will be calculated based on observed data. If 3 observed components show improvement, it is assumed that the 4th domain will not worsen.

- For ASAS5/6:

- If at least 5 of the 6 components have observed data collected, the ASAS5/6 response will be calculated based on observed data. If 5 observed components show improvement, it is assumed that the 6th domain will not worsen.
- If there are fewer than 5 components with observed data at a given post-Baseline visit, then imputation methods will be applied, consistent with the pre-defined approach for handling intercurrent events. See Section 8.2.1.1 for further details.

For multiple imputation of non-composite binary secondary or other endpoints, the standard multiple imputation (MI) methods (See Section 4.2.1.4.1) will be implemented on the raw score (eg, BASDAI for the BASDAI50 endpoint) before deriving the binary endpoint based on the imputed score.

4.2.1.3 Composite Estimand - Non-Responder Imputation (NRI) analysis

This is the primary analysis for the ASAS40 primary efficacy endpoint.

In the NRI analysis, study participants will be classified as ‘non-responders’ (ie, as if they have not responded to the treatment) at all time points after the date of discontinuation of study treatment for any reason.

In addition, for all endpoints except the ASAS response for which the response is still calculable when there is only 1 component with missing data (see Section 4.2.1.1), study participants will also be classified as ‘non-responders’ at all timepoints they had missing data.

4.2.1.4 Modified Composite Estimand - Multiple Imputation (MI)

This section describes the algorithms to be implemented for the MI – Markov-Chain Monte Carlo (MCMC)/Monotone Regression procedures for non-composite binary and composite binary endpoints.

Unless mentioned otherwise, all study participants from the population set of interest (eg, the randomized set) should be included in the MI steps.

4.2.1.4.1 Non-composite binary endpoints (Modified Composite Estimand)

For non-composite binary endpoints, the MI method will be applied as follows based on raw values:

- Step 1: Any observation after date of discontinuation of study treatment for any reason will be set to missing.
- Step 2: Create a dataset, one for each treatment group, of study participants with observed values and those needing estimation by multiple imputation. For the imputation step, missing values will include non-monotone missing values (ie, intermittent missing values between completed assessments) and monotone missing values (ie, where all study participant data is missing after a given time point).
 - **Step 2a:** First, the intermittent missing values in each dataset will be imputed using the MCMC method with multiple chains, monotone missing data imputing pattern, and non-informative priors for all parameters. Unless specified differently, the first 200 iterations will not be used (the ‘burn-in’ option). A total of 100 sets of imputations will be

performed. The seed used for these imputations will be 2017 and all other multiple imputation procedures described in this SAP will use this same seed as well.

- **Step 2b:** If an imputed value falls outside of the pre-defined range of values for the given variable, the value will be truncated to be within the predefined range of values for the endpoint of interest. For example, the imputed value for BASDAI will be updated to 0 or 10 in the case of an imputed value less than 0 or greater than 10, respectively (see [Table 4–2](#)).

The resulting 100 imputed data sets will have a monotone missing data pattern and will be imputed using a method for monotone missingness:

- **Step 2c:** For monotone missing data, monotone regression will be used to impute missing data. A separate regression model is estimated for each variable with missing values (ie, measurement at each time point). Based on the resulting model, a new regression model is then drawn and is used to impute the missing values for the variable. Since the data set has a monotone missing data pattern, the process is repeated sequentially for variables with missing values. The procedure will be based on the 100 imputed datasets generated from the MCMC procedure and will be performed by Imputation.
- **Step 2d:** If an imputed value falls outside of the pre-defined range of values for the given variable, the value will be truncated to be within the predefined range of values for the endpoint of interest.

The SAS® PROC MI procedure will be used for the imputation.

In both cases, the imputation model will include, in the following order: prior TNF α inhibitor exposure, region, the value at Baseline and at each post-Baseline visit (prior to the week of interest).

The visits to include in the MCMC and monotone regression steps will be the same, and will correspond to all data available at the time of the analysis, as specified below:

- For dry-runs conducted prior to the Week 24 interim analysis, all weeks up to Week 24 will be included,
- For the Week 24 interim analysis, all weeks up to Week 24 will be included,
- For the Week 52 interim analysis and final analysis, all weeks up to Week 52 will be included.

The stratification factors (prior TNF α inhibitor exposure and/or region) may be dropped from the imputation model to facilitate model convergence if required (and this holds true for all imputation models). The post-Baseline values will need to be specified in chronological order in the imputation model so that the SAS® PROC MI imputes variables from left to right (ie, the Week 1 value will be first imputed using regression based on Baseline value, and then the Week 2 value will be imputed using regression based on Baseline and Week 1 values, etc.). Study participants with missing Baseline will also be included in the imputation step.

The resulting datasets for each treatment arm will be combined into one complete dataset based on each of the 100 imputations (containing 100 times the number of study participants analyzed).

The imputation model based on the MCMC method for intermittent missing values will only allow multivariate normal variables. Therefore, region which has 4 levels will be re-coded as indicator variable:

One indicator variable (region1) will be defined as 0 for regions other than North America and 1 for North America. Two more indicator variables (region2 and region3) will be defined similarly replacing North America with Eastern Europe and Western Europe respectively. In the VAR statement of the imputation model, the indicator variables will be ordered as follows: region1 region2 and region3. In the eventuality that two regions required to be pooled due to a low percentage of study participants randomized in one region (see Section 3.8), the indicator variables defined above will be revised accordingly.

- One indicator variable will be defined for the prior TNF α inhibitor exposure stratification variable: will be coded as 1 for yes and 0 for No.

To maintain consistency with the MCMC method for intermittent missing values, these indicator variables will also be used in the monotone regression step for monotone missing values and treated as continuous variables.

- Step 3: For each of the 100 complete imputed data set obtained from Step 2, the binary responder variable will be derived. In practice, the value at the week of interest (eg, Week 16) in the imputed data sets will be used to categorize the study participant as a responder or not. If study participants have a treatment discontinuation due to AE or lack of efficacy, then the endpoint will be changed to “non-response” for all visits after the IE date.
- Step 4:
 - For secondary efficacy endpoints: For each of the datasets obtained in Step 3, the responder rate will be analyzed using a logistic regression model with factors of treatment group, region, and prior TNF α inhibitor exposure as fixed effects. The suitability of including region and prior TNF α inhibitor exposure at Baseline as fixed effects will be assessed using goodness-of-fit tests (Deviance and Pearson’s and Hosmer-Lemeshow) and added if appropriate and allows model convergence.
 - For other efficacy binary endpoints: At each timepoint, the mean proportion of the responders and 95% CIs will be calculated from the imputed datasets using SAS® PROC MIANALYZE.
- Step 5 (for secondary efficacy endpoints only): The results obtained from the 100 logistic regression analyses in step 4 (ie, the adjusted responder rates for each treatment group and the corresponding 95% CI, the odds ratio of the treatment comparison and corresponding 95% CI) will be combined for overall inference using Rubin’s rules, which account for the uncertainty associated with the imputed values (Rubin, 1987). This will be done using SAS® PROC MIANALYZE. The method for determining the degrees of freedom when combining results will be the freedom default Rubin’s method.

4.2.1.4.2 Composite binary Endpoint (Modified Composite Estimand)

For composite binary endpoints, the MCMC/monotone regression method described above in Steps 1 to 3 for handling intermittent and monotone missing data will be performed separately for each individual component variable. As mentioned above, study participants with missing

Baseline will also be included in the imputation step. Refer to Section 4.2.1.1 for details on the handling of missing and zero Baseline for ASAS endpoints.

Then, based on the multiply imputed data sets obtained for each component, the binary response will be derived as follows:

- The 100 data sets obtained for each component will be merged by imputation number and study participant number.
- For each of the 100 complete imputed data sets, the binary endpoint will be derived for each study participant/visit based on the component values. In the case of the ASAS40 and ASAS20 where only one component value (among the 4) is missing at a visit, the response will be derived without using the imputed value of the missing component.
- If study participants have a treatment discontinuation due to AE or lack of efficacy, then the response associated to the binary endpoint will be changed to “non-response” for all visits after the IE date.

Procedures described for Step 4 to Step 5 will then follow.

For the primary endpoint, the ‘burn-in’ option in PROC MI will be set to the default value (200 in this case). The convergence of the MCMC will be assessed graphically, and the results will be provided in a SAS® output.

In addition, for ASDAS-MI endpoint, the following actions should also be taken:

- in step 2b and 2d, any imputed CRP values $<0.5 * \text{the LLOQ (0.1)}$ will be reset to 0.05 after each MCMC and monotone steps to account for potentially different LLOQs across individuals,
- when determining ASDAS-MI, ASDAS-CRP values <2 should be reset to 2 only after the monotone regression imputation step (i.e., after Step 2d) prior to calculation of the composite score.

4.2.1.5 Calculation of adjusted responder rates, odds ratio and CIs for binary endpoints.

Estimates of the adjusted responder rates for each treatment group and the associated standard errors are obtained from the logistic regression in Step 4 on the logit scale and as such are assumed to follow a normal distribution. These estimates will be combined using Rubin’s rules and the combined estimates and associated SEs will be used to construct 95% CIs on the logit scale. The combined estimates and 95% CIs on the logit scale will be back-transformed using the inverse logit link function to obtain the adjusted responder rates (%) and associated 95% CIs.

Some key points to consider relative to the calculation of the odds ratios and corresponding confidence intervals. As the estimates of the odds ratios from the logistic regression model in Step 4 follow a lognormal distribution, a log transformation is needed to normalize these 100 odds ratio estimates since the procedures for combining results from multiple imputed datasets are based on the assumption that the statistics estimated from each imputed dataset are normally distributed. Therefore, the log of the odds ratio estimates from the logistic regression model are used when combining into a single inference (Step 5). Additionally, the standard errors (SE) for the odds ratios are transformed as follows:

$$SE = \frac{\log(UCL) - \log(LCL)}{2Z_{\alpha/2}}$$

where UCL and LCL are the upper and lower confidence limit, respectively, for the CI of the odds ratio from the logistic regression model, and $Z_{\alpha/2}$ is the relevant critical value from the standard normal distribution (1.96 for a 95% CI). The estimates of the log odds ratio for bimekizumab relative to placebo and the corresponding upper and lower confidence limits will be provided. The odds ratio will be then estimated by exponentiating the estimate of the log odds ratio. The odds ratio and the confidence limits of the odds ratio will be estimated as follows:

$$OR = \exp(Log\ odds\ ratio\ estimate)$$

$$LCL = OR * \exp(-SE * Z_{\alpha/2})$$

$$UCL = OR * \exp(SE * Z_{\alpha/2})$$

where OR is the back-transformed estimate of the odds ratio just described, SE is the standard error of the log odds ratio and $Z_{\alpha/2}$ is the relevant critical value from the standard normal distribution (1.96 for a 95% CI). For mean proportion of responders or responder rates, the LCL will be truncated at 0. These calculations will be done such that odds ratios and corresponding CIs are calculated for the odds ratio of bimekizumab versus placebo.

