 - For the median, Q1, Q3, minimum and maximum the procedure outlined above for the other endpoints will be followed (based on logged values). And the resulting summary statistics will finally be back-transformed to obtain the values on the original scale.

- In Step 4, the analysis will be done on the change from Baseline, and the model will be an ANCOVA model with treatment group, region, and prior TNF α inhibitor exposure as fixed effects and the Baseline value as covariate.
- In Step 5, the results obtained from the 100 ANCOVA analyses in Step 4 (ie, the Least Square Means for the treatment difference and the 95% CI for the contrasts) will be combined with Rubin's rules.

For other continuous efficacy endpoints, the following steps will apply:

- The same Steps 1 to Step 5 as the ones described for non-composite binary efficacy endpoints (but excluding Step 3) will be implemented.
- For ASDAS-CRP endpoint only, the following should also be considered:
 - after each MCMC and monotone steps to account for potentially different LLOQs across individuals: any imputed CRP values $<0.5 * \text{the LLOQ (0.1)}$ will be reset to 0.05.
 - any imputed CRP values <2 will be rest to 2 only one time after monotone regression imputation step and immediately prior to calculation of the component score.
- The same Step 4 and Step 5 as those described above for secondary endpoints (but excluding the “Step 4 for hs-CRP only”) will be implemented.

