8.2.1.3 Ankylosing Spondylitis Disease Activity Score major improvement (ASDAS-MI)

The ASDAS-CRP consists of a number of assessments which are scored by the study participant and physician and multiplied by a proven formula (van der Heijde et al, 2009) as shown below:

- 0.121 x Back pain (BASDAI Question 2 result)
- 0.058 x Duration of morning stiffness (BASDAI Question 6 result)
- 0.110 x Patient's Global Assessment of Disease Activity (PGADA)
- 0.073 x Peripheral pain/swelling (BASDAI Question 3 result)
- 0.579 x (natural logarithm of the (hs-CRP [mg/L] +1))

Back pain, PGADA, duration of morning stiffness, peripheral pain/swelling and fatigue are all assessed on a numerical scale (0 to 10 units) (Lukas et al, 2009). If the hs-CRP value is <2 mg/L, the constant value of 2 mg/L should be used in the calculation. The sum of these weighted components gives the ASDAS-CRP.

For analyses with imputation of missing data, the imputed value for ASDAS-CRP will be based on the imputed values for the individual components.

For observed case analyses, if any individual component score is missing, then the ASDAS-CRP will be set to missing.

Disease activity categories based on ASDAS-CRP are as follows:

- ASDAS-Inactive Disease (ASDAS-ID): ASDAS-CRP <1.3
- ASDAS-Low Disease (ASDAS-LD): ASDAS-CRP ≥1.3 to <2.1
- ASDAS-High Disease Activity (ASDAS-HD): ASDAS-CRP ≥2.1 to ≤3.5
- ASDAS-very High Disease Activity (ASDAS-vHD): ASDAS-CRP >3.5

The variables related to ASDAS improvement are defined as follows:

- ASDAS-Clinically Important Improvement (ASDAS-CII): ASDAS-CRP reduction (improvement) of ≥1.1 relative to Baseline
- ASDAS-Major Improvement (ASDAS-MI): ASDAS-CRP reduction (improvement) of ≥2.0 relative to Baseline

For both ASDAS disease category and ASDAS improvement variables, multiple imputation methods will be used to impute the ASDAS-CRP value and then dividing into the appropriate category or improvement groups.

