For all these variables, the results based on the NRI will be combined with the ones obtained on OC and from the MI analysis in one single table.

In addition, a line plot by treatment group will be produced over time for some of the endpoints, that are part of the sequential testing procedure, based on NRI results, including the following binary variables: ASAS40 responder rate, ASAS40 responder rate in the TNF alpha inhibitor naïve study participants, ASAS20 responder rate, ASAS5/6 responder rate, ASAS-PR responder rate, and ASDAS-MI responder rate.

Continuous other efficacy variables that are components of the primary endpoint will be analyzed using the reference-based MI estimand and procedure described in Section 8.1.4.3.

For the continuous and categorical other efficacy variables (not including change from Baseline in WPAI-SHP, ASspiMRI-a (Berlin modification) score, and SPARCC score, and EQ-5D-3L Utility scores), the following estimand structure will be defined:

- Hypothetical Estimand (Section 4.2.1.7) – MI:
 - Population = Study participants enrolled according to the protocol-specified inclusion/exclusion criteria and randomized to IMP
 - Study participant-level outcome = The given variable and time point being summarized
 - Intercurrent event handling = An intercurrent event is defined as discontinuation of study treatment prior to the time point being summarized. This estimand targets the treatment difference in a scenario where the intercurrent event does not occur, such that outcomes for study participants without an intercurrent event are as observed at the given time point, and outcomes for study participants with an intercurrent event are treated as though they had completed the randomized study treatment through the time point being summarized
 - Population-level summary measure = Unadjusted mean.

The same imputation strategy for handling missing data as the one used for the secondary continuous efficacy endpoints as described in Section 8.2.2 will be implemented. Missing data for ASDAS status endpoint will also be imputed using MI, and the imputation will be done on the components of ASDAS-CRP prior to calculating ASDAS-CRP and categorizing ASDAS status. The mean proportion of responders in the multiply imputed data sets (with the associated 95% CI based on SE) will be displayed for each ASDAS category.

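### For the MI analysis of ASDAS-MI, SAP Section 4.2.1.4.2 puts the floor of 2 on the ASDAS-CRP score, where hs-CRP below 2 mg/L is meant

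*SAP*

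**What the plan says.** Three places in the SAP deal with the constant 2.

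- **Section 4.2.1.4.2** (composite binary endpoints, modified composite estimand) adds two rules for ASDAS-MI. The first concerns imputed CRP below half the LLOQ. The second says that "ASDAS-CRP values <2 should be reset to 2 only after the monotone regression imputation step", and places this step "prior to calculation of the composite score".
- **Section 8.2.1.3** defines the score: "The sum of these weighted components gives the ASDAS-CRP". Inside that definition, "If the hs-CRP value is <2 mg/L, the constant value of 2 mg/L should be used in the calculation".
- **Section 4.2.1.7**, for the continuous ASDAS-CRP endpoint, says that "any imputed CRP values <2 will be rest to 2 only one time", after the monotone regression step and just before the score is calculated.

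On how the score is imputed, Section 8.2.1.3 states that in analyses with imputation ASDAS-CRP rests on the imputed individual components. Section 8.3.2 says the same for ASDAS status: "the imputation will be done on the components of ASDAS-CRP prior to calculating ASDAS-CRP and categorizing ASDAS status". Section 8.2.1.3 defines ASDAS-MI as a fall in ASDAS-CRP of 2.0 or more from Baseline. Table 4-1 makes NRI primary and MI supportive for binary secondary endpoints in the hierarchy, of which ASDAS-MI is one.

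**The concern.** ASDAS-CRP is the SAP's name for the score, not for the laboratory value. The same constant is therefore attached to the score in one section and to CRP in two others. The Section 4.2.1.4.2 rule also conflicts with its own timing: it resets a score before the score has been calculated.

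A programmer who followed the named variable rather than the timing would floor the Week 16 score at 2. A supportive analysis tests robustness to missing data only if the responder definition stays the same. With a score floor that definition would change, and a coding artefact could be taken for sensitivity to missing data. Unlike the rule in Section 4.2.1.7, the rule is not limited to imputed values, so read literally it would also reach participants with complete data.

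**Working it through.** **The plan's own figure.** Section 2.4.2 gives 98% power for ASDAS-MI, with 36.0% against 13.8% responders, 200 against 100 participants and a two-sided 0.05 chi-square test with continuity correction. Recalculation gives 98.6% with the correction and 99.1% without, so the figure is reproduced. It does not depend on the reset rule.

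**Inputs, all from Section 8.2.1.3.** Item weights are 0.121 (back pain), 0.058 (duration of morning stiffness), 0.110 (patient's global assessment) and 0.073 (peripheral pain/swelling). The CRP term is 0.579 × ln(hs-CRP + 1), and hs-CRP below 2 mg/L is entered as 2. Response is a reduction of at least 2.0.

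**Step 1: lowest attainable score with the CRP floor.** All items are 0 and hs-CRP is 2: 0.579 × ln(2 + 1) = 0.636.

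**Step 2: Baseline needed for response to be possible.**
- Floor on hs-CRP: 0.636 + 2.0 = 2.636.
- Floor of 2 on the score: 2.0 + 2.0 = 4.0.

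**Step 3: who would be reclassified.**
- Baseline below 2.64: response is impossible under either rule, so nothing changes.
- Baseline from 2.64 to below 4.0: response needs a Week 16 score of at most Baseline − 2.0, which is below 2. The floor lifts that score to 2, and the reduction becomes Baseline − 2, which is less than 2.0. Every such responder is lost.
- Baseline 4.0 or above: a Week 16 score below 2 is lifted to 2, but the reduction is still at least 2.0. Nothing changes.

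**Step 4: an example.** The weights sum to 0.121 + 0.058 + 0.110 + 0.073 = 0.362.
- Baseline, all four items 7 and hs-CRP 8 mg/L: 0.362 × 7 + 0.579 × ln 9 = 2.534 + 1.272 = 3.81.
- Week 16, all four items 2 and hs-CRP at most 2 mg/L: 0.362 × 2 + 0.636 = 1.36.
- Reduction 3.81 − 1.36 = 2.45, a responder. With the score floored at 2 it is 3.81 − 2 = 1.81, a non-responder.

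**Step 5: fit with the scale.** The SAP's categories include "ASDAS-Inactive Disease (ASDAS-ID): ASDAS-CRP <1.3". A score floored at 2 could never reach that category. The rule covers ASDAS-MI only, so this does not affect the ASDAS status tables, but it shows that 2 is not a sensible floor for the score.

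**The case against.** The strongest reply is that nobody could carry out the wrong reading without ignoring the rest of the text. Imputation is done separately for each component, the component data sets are merged, and the endpoint is derived from component values. The neighbouring ASDAS-MI rule concerns CRP, the parallel rule in Section 4.2.1.7 names CRP, and Section 8.2.1.3 gives the constant in mg/L of hs-CRP. This stands: the intended meaning is clear, and the defect is one of wording.

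A reader might still infer real ambiguity from the sentence in Section 8.2.1.3 that "multiple imputation methods will be used to impute the ASDAS-CRP value and then dividing into the appropriate category or improvement groups". The documents do not support that. The same section explains that the imputed score is built from imputed components.

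A reader might also infer that the whole high disease activity category (2.1 to 3.5) would be shut out by the literal rule. That goes too far, because Baselines from 2.1 to below 2.64 cannot respond under the correct rule either.

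Finally, a miscoding might show itself. Section 8.3.2 puts NRI, observed-case and MI results in one table. MI only replaces some NRI non-responses with imputed outcomes, so, apart from the Section 8.3.1.5 rule that sets CRP of 500 mg/L or more to missing, an unadjusted MI rate below the NRI rate would signal an error. This helps only if the floor had been applied to observed scores as well. If it touched imputed values alone, the MI rate would not fall below NRI and the comparison would show nothing.

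**Conclusion.** The rule in Section 4.2.1.4.2 is wrong as written and is evidently a slip for hs-CRP. Followed literally, it would raise the Baseline at which ASDAS-MI is attainable from 2.64 to 4.0. These thresholds are exact, follow from the SAP's formula and need no outside assumption.

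The exposure is confined to the supportive modified-composite MI analysis of ASDAS-MI and its by-visit MI summaries. It would be wrong to infer that the confirmatory result is at risk: the NRI analysis, the testing hierarchy and the power calculation do not use this rule. Nor can a distorted responder rate or odds ratio be stated from the SAP. It gives no Baseline distribution of ASDAS-CRP, so any such figure would rest on assumed inputs. Severity: minor.

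**What to change.** In Section 4.2.1.4.2, replace the reset of the score with a rule on the laboratory value, for example: *any hs-CRP value below 2 mg/L, observed or imputed, is set to 2 mg/L once, after Step 2d and immediately before ASDAS-CRP is calculated*. This agrees with Sections 4.2.1.7 and 8.2.1.3. Adding the unit in Section 4.2.1.7 would be tidy but is not essential, because Section 8.2.1.3 already gives it.

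The cost is one phrase. Data, hierarchy and primary analysis do not change. The program for the MI analysis of ASDAS-MI should be checked to confirm that the floor is applied to hs-CRP. Comparing unadjusted MI and NRI responder rates is an optional extra check, within the limits given above.
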